**Assessments.** We will have four assessment points: baseline (pre-test), 12, 24, and 36-months post-intervention initiation. All Assessments will take place at the child's home with each lasting about 60 minutes. Although all the children will be attending school, and we expect all of them to be English-speaking (the instructional language in all Ugandan schools), assessments will be conducted in English or Luganda (local language) depending on participants' English proficiency. All interviewers will be fluent in English and Luganda. Questions will be translated from English to Luganda and back-translated by a certified translator from a local University (Department of Languages) following standard procedures. Drs. [name] and [name] (fluent in Luganda and English) will cross-check all translated assessments. All interviewers will receive a highly structured and intensive training conducted by Drs. [name] and [name]. All measures used have been or will be pre-tested and made culturally appropriate to the Ugandan context. For questions measuring sensitive behaviors (i.e., sexual risks), we will use Audio Computer-Assisted Self-Interviews (ACASI) where the participant takes the survey herself on a mini laptop. Non-sensitive questions will be interviewer-administered.

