#### **Selection of Participants**

The target population for this study are older adolescent girls (ages 15-17 at enrollment), in secondary school and living within the four districts of Uganda: Masaka, Rakai, Lwengo and Kalungu. HIV prevalence in this region is 9.8%, compared to other regions in Uganda (7.3%).

**Inclusion Criteria:** Specifically, for an adolescent to be included in the study, she will have to meet the following criteria: (1) female; (2) enrolled in her first year of secondary school (senior

1) in Rakai, Masaka, Lwengo or Kalungu districts; (3) age 15-17 years; (4) living within a family (broadly defined and not an institution or orphanage, as those in institutions have different familial needs).

**Exclusion criteria:** Girls are ineligible if: (1) they have a cognitive or severe psychiatric impairment that would prevent comprehension of study procedures as assessed during the Informed Consent process (see Recruitment and Consent Section) or; (2) they are unwilling or unable to commit to completing the study.

We will not exclude girls because of their HIV, STI and/or pregnancy status and the analysis will be adjusted to account for these baseline factors. Girls testing positive for HIV, STI (Gonorrhea, Trichomonas, or Chlamydia) or pregnancy will be referred for care and support (see *Study Population* above). A plethora of services, including access to free antiretroviral therapy (ART), and counseling exist for children and adults living with HIV in the study region. We will follow up with all girls who test positive for HIV or an STI within 30 days of referral, to check on their engagement in care. For girls who test HIV positive, engagement in care will be verified annually using clinical and viral load records.

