Given the research team's experience with the sets of economic empowerment studies informing this R01, we anticipate that most caregivers may not be English-speaking. For that reason, the caregivers' consent forms will be translated into Luganda (the local language spoken in the study area) from English, and then back-translated into English by a certified translator at a local University (Makerere, Nkozi or Mutesa Royal University, Dept. of Languages). The PI ([name]), the in-country Co-I ([name]) and the in-country Project Coordinator ([name]) are all fluent in Luganda. This will be helpful in cross-checking the translated documents.

Additionally, although all the children will be English-speaking (English is the official and instructional language used in schools in Uganda), some may be more comfortable using Luganda (local dialect). Therefore, the assent process will be conducted in English or Luganda (local language) depending on participants' English proficiency. Just like with the caregivers' consent forms, all adolescents' assent forms will be translated from English to Luganda and back-translated by a certified translator from a local university (Makerere, Nkozi or Mutesa 1 Royal University Department of Languages).

The PI, in-country Co-I ([name]), the in-country Project Coordinator ([name]), or research assistants will read and explain the consent form to the caregiver. In signing the consent form, the caregiver will be consenting to the adolescent's participation in the study screening and enrollment process (which will include having her blood drawn to ascertain HIV, urine testing to determine pregnancy, and high vaginal swab to establish the status on the three STIs to be tested Gonorrhea, Trichomonas and Chlamydia); recruitment and participation in the study (if inclusion criteria is met); and also authorizing access to the adolescent's school records by the Project Coordinator and/or the PI. Each adolescent will also go through the same process. They will each be read their assent forms before signing.

During the consent process, the Project Coordinator and either the PI ([name]) or Co-I ([name]) or research assistant will explain the study procedures to the caregivers. After the team (Project Coordinator and either PI or Co-I) is assured that the caregivers fully understand what would be expected of the adolescent and the caregiving family, the caregiver will be allowed to sign the consent form.

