### **Potential Risks**

There are no major risks involved, however, an adolescent may feel embarrassed or uncomfortable during the recruitment and interview process when answering sensitive and personal questions, with urine collection for pregnancy testing, taking blood for HIV and/or high vaginal swabs for STIs (Gonorrhea, Trichomonas and Chlamydia). The process of blood draw may cause some discomfort, bleeding, or bruising where the needle enters the body, and in very rare cases, fainting or infection. First and foremost, interviewers will make it explicitly known to the participants that they may refuse to answer a question or decline to undergo a procedure, at any time. This will also be explained in writing on the consent/ assent forms. If an adolescent tells the interviewer that she is uncomfortable with a particular topic, that she prefers not to discuss a particular topic, or feels she cannot participate in the biomarker process the interviewer will move on to the next question/part of the interview.

Additionally, for questions measuring sensitive behaviors like sexual risk-taking and mental health, we will use audio computer-assisted self-interviews (ACASI) where the participant takes the survey herself on a mini laptop/iPad. This will provide additional privacy for the participant, can be programmed in multiple languages, and is designed for use by both literate and pre-literate populations. Research assistants will be available for any participant experiencing technical difficulty with the use of the computer-assisted interview.

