Our primary interest is to estimate the marginal or population-average effects of intervention participation on HIV risk outcomes rather than the effect for a hypothetical average subject or school. Moreover, within-subject and within-school HIV risk outcome correlations are considered nuisance parameters rather than quantities of interest to be modeled explicitly. Accordingly, generalized estimating equations (GEE) will be used to perform the proposed primary analyses to test Hypotheses H1A-H1C. These hypotheses will be tested by three pairwise planned time-averaged comparisons of post-baseline measurements. Alpha ( $\alpha$ ) will be set at  $.05/3=.017$  for these three planned comparisons to maintain a nominal  $\alpha=.05$ . Any additional post-hoc comparisons (e.g., paired comparisons of groups at each time point) will maintain nominal alpha of .05 through the use of simulation-based stepdown multiple comparison methods. The alternating logistic regression (ALR) approach implemented in SAS PROC GENMOD will be used to address the 3-level clustering of observations within participants and participants within schools. Though GEE estimates are consistent even if the correlation structure is misspecified, GEE's statistical efficiency improves as the working correlation structure more closely approximates the actual correlation structure; therefore, various correlation structures suitable for the study's design will be considered (e.g., exchangeable; nested-1). The QIC statistic will be used to select the final correlation structure. Randomization strata indicators will be included as covariates as required by the stratified randomized design to obtain unbiased inferences. Additional covariates (e.g., HIV serostatus) will be included if they improve QIC. Robust Huber-White "sandwich" standard errors will be used to obtain correct inferences even if the chosen correlation structure remains slightly misspecified. GEE case deletion diagnostics (e.g.,

DFBetas, Cook's *D*) will be used to investigate whether influential cases are present; if such cases are found, results will be reported with and without influential cases included.

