**Primary analyses for Specific Aim 2.** For Specific Aim 2, *Elucidate the effects of the Suubi4Her interventions on behavioral health functioning (i.e., depression, self-efficacy and hopelessness) and examine the effects of these variables as potential mechanisms of change, mediating the relationship between each intervention and HIV risk reduction*, we hypothesize that following baseline participants in:

1. H2A: YDA will have higher mean mental health functioning vs. control participants;
2. H2B: YDA+MFG will have higher mean mental health functioning vs. control participants, and
3. H2C: YDA+MFG will have higher mean mental health functioning vs. YDA participants.

[figure not shown]
The same GEE-based approach as described above in the primary analysis for Specific Aim 1 will be used to test H2A-H2C, except that instead of the odds of a binary outcome being estimated, the GEEs for H2A-H2C will employ appropriate distributions and link functions suitable for modeling the means of continuous mental health outcomes (e.g., normal distribution and identity link function). Robust Huber-White "sandwich" standard errors will be used to obtain correct inferences even if the chosen correlation structure remains slightly misspecified or if residual distributions are not perfectly normal or homoscedastic.

**Aim 3: Evaluate the cost-effectiveness of each intervention condition.** Following standard practice of measuring cost-effectiveness of interventions, we will measure costs on a per person basis. The intervention costs will include all program costs, including not just the YDA savings match, but also all costs incurred for running the program. Research costs will not be included. Data on the savings match costs will be readily available from the management information system. Data on costs of other program elements will be drawn from project administrative records and collected throughout the intervention period. In the analyses, costs from multiple years will be adjusted for inflation, depreciation, and discounting.

We will estimate how much *Combined Intervention (YDA + MFG)* vs *YDA-alone* increased particular outcomes, such as schooling. The per-person costs of *YDA + MFG*, and *YDA alone* will then be divided by the relevant effect sizes to produce estimates of cost-effectiveness.

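### Adjustment for baseline HIV, STI and pregnancy status is promised without condition in one section and left to QIC in another, so the primary covariate list is not fixed in advance

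*Combined protocol and SAP*

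**What the plan says.** The document makes two statements about covariates.

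- *Selection of Participants*: girls are not to be excluded for "HIV, STI and/or pregnancy status and the analysis will be adjusted to account for these baseline factors". No condition is attached. The same section repeats the commitment in a sentence about girls who are HIV positive.
- *Data Analysis Plan and Statistical Procedures*, primary analyses for Specific Aim 1: "Randomization strata indicators will be included as covariates as required by the stratified randomized design to obtain unbiased inferences". The next sentence reads: "Additional covariates (e.g., HIV serostatus) will be included if they improve QIC". QIC also selects the correlation structure.

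The Aim 2 text carries the rule over: "The same GEE-based approach as described above in the primary analysis for Specific Aim 1 will be used to test H2A-H2C".

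The tests are "three pairwise planned time-averaged comparisons of post-baseline measurements". A baseline measurement is scheduled, since "We will have four assessment points: baseline (pre-test), 12, 24, and 36-months post-intervention initiation", but the analysis section does not say how the baseline value of an outcome enters the model.

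**The concern.** One section says the adjustment will be made. The other says it will be made if a data-driven criterion favours it, and uses one of the three promised factors, HIV serostatus, as its example of a conditional covariate. STI and pregnancy status are not named in the analysis section at all. The candidate list is open, with no search order and no required size of QIC improvement. No separate adjusted analysis is described to which the unconditional statement could refer.

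What is at stake is pre-specification. A reader cannot tell beforehand which model is primary for H1A-H1C and H2A-H2C, and the covariate set could differ from outcome to outcome. The section on adverse events has investigators examining preliminary outcome data quarterly. It does not say that they see these data by arm, but it is a reason to close the list early.

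A second open choice sits beside the first: whether the baseline value of the outcome is a covariate. For Aim 1 the two overlap, because STI is among the outcomes.

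**Working it through.** **1. The two rules side by side.** The documents give no figure to reproduce here. With only the three promised statuses as candidates, the QIC rule allows 2^3 = 8 covariate sets, of which 1 meets the unconditional statement. Crossed with the two correlation structures named as examples, that is 8 x 2 = 16 specifications. Because the list is open, these counts are minimums.

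**2. How often QIC would keep the statuses (simulation).** From the documents: 14 schools and 420 girls per arm, so 3 x 14 = 42 schools and 420/14 = 30 girls per school; three post-baseline waves; alpha .05/3. Assumed: four strata of 12, 12, 9 and 9 schools with arms balanced within strata; a logit model with girl variance 1.0 and school variance 0.1; outcome prevalence about 10% or 20%; baseline STI 10%, pregnancy 3%, and HIV 2% or 9.8% (9.8% is the document's regional figure, not one for girls aged 15-17). The fit was independence GEE with arm and strata always included and a sandwich variance by school; the planned alternating logistic regression was not simulated. QIC = -2Q + 2 trace(Omega V_R). There were 1,000 trials per setting (995 usable in one). Ranges cover one-at-a-time and best-subset searches for the all-three column.

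| Assumed odds ratio, status to outcome | All three kept | HIV kept |
|---|---|---|
| 1 | 0.3-1.3% | 18-22% |
| 1.5 | 9-34% | 33-83% |
| 2 | 43-81% | 61-99.6% |
| 3 | 86-98% | 90-100% |

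**3. Effect on the test result.** For YDA+MFG against control, using t with 39 df, the significance call differed between the QIC-chosen and the fixed list in at most 0.6% of trials. Rejection rates under no effect differed by at most 0.3 percentage points. (Both lists ran above .0167 alike because the sandwich standard error was uncorrected with 42 schools; that is a separate matter.) Across all eight sets the call was not unanimous in 0.2-2.8% of trials with no effect and in 2.7-7.0% at about 70% power.

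A simpler null check without clustering (420 per arm, 15% base risk, status prevalences 5-8%, odds ratios 1.5-3, AIC-type selection standing in for QIC, 3,000 runs) gave rejection rates of 0.017 unadjusted, 0.017 fully adjusted and 0.016 after selection. Reporting the most favourable of the eight sets gave 0.021.

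**4. Baseline score in Aim 2.** Assumed: ICC .03, effect 0.2 SD, correlation r between assessments either constant or decaying as r, r^2, r^3.

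v0 = mean of the 3 x 3 wave correlation matrix; v1 = v0 - (mean baseline-to-wave correlation)^2.

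- Constant r = .5: v0 = (3 + 6 x .5)/9 = .667; v1 = .667 - .25 = .417.
- Constant r = .3: v0 = (3 + 6 x .3)/9 = .533; v1 = .533 - .09 = .443.
- Decaying r = .3: v0 = (3 + 4 x .3 + 2 x .09)/9 = .487; mean baseline correlation = (.3 + .09 + .027)/3 = .139; v1 = .487 - .019 = .467.

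If baseline explains school and girl variance equally, SE = sqrt(2 x (ICC x v + (1-ICC) x v/30)/14). If it does not predict a persistent school effect, SE = sqrt(2 x (ICC + (1-ICC) x v/30)/14). Power is from the noncentral t at two-sided .05/3, with 39 df unadjusted and 38 df adjusted.

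| Correlation | Equal: SE | Equal: power | Persistent school effect: SE | Persistent: power |
|---|---|---|---|---|
| Constant .5 | .0770 to .0609 | 54 to 78% | .0858 to .0788 | 44 to 52% |
| Constant .3 | .0689 to .0628 | 66 to 75% | .0822 to .0796 | 48 to 51% |
| Decaying .3 | .0658 to .0645 | 70 to 72% | .0808 to .0803 | 49.6 to 50.1% |

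These gains assume that the score would otherwise be left out. When it was offered to QIC in a Gaussian simulation, it entered in 100% of trials at constant r of .1 or more and at decaying r of .3 or more, and in 75-76% at decaying r = .1.

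**5. Marginal versus conditional odds ratio.** With an assumed conditional odds ratio of 0.60, base risk 15%, covariate prevalence 2-20% and covariate odds ratio 2-10, the marginal odds ratio runs from 0.60 to 0.66. The covariates admitted can therefore change slightly what the Aim 1 estimate means.

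**The case against.** The best defence is that this is a loose sentence in an eligibility section set against an operative analysis section. The former speaks of the analysis, not of the primary model, and the repeated phrase concerns effects in HIV-positive girls. The QIC criterion is itself stated in advance. Comparing post-baseline measurements between randomized arms is valid without baseline adjustment, and the test results barely move.

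Much of this stands. Three stronger readings are tempting, and the documents do not support them:

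- A reader might infer that the two statements can never govern the same model. They conflict only when a status fails to improve QIC.
- A reader might infer that the promised adjustment would usually fail. The documents give no associations and no prevalences of these conditions in the enrolled girls, and the simulated range is too wide to say.
- A reader might infer that QIC selection biases the comparison or inflates type I error. The checks show no such effect when the rule is applied mechanically.

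What does not stand is the suggestion that the unconditional statement refers to some other analysis, because none is described. Stating the criterion in advance does not fix the candidates or the resulting list.

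**Conclusion.** The inconsistency is certain on the text and should be repaired; it is a pre-specification defect. Its effect on significance calls through the three statuses is very small, at most 0.6% of simulated trials under the assumptions above.

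The only sizeable gain from a fixed list lies in the continuous Aim 2 scores, where always adjusting for baseline adds about 0.5 to 24 points of power. The 24-point figure is the most favourable case: r = .5 at every wave, school variance explained as well as girl variance, and a team that would never have offered the score to QIC. It should not be read as the expected cost of the present plan. For rare binary Aim 1 outcomes the benefit is a defined primary model, with little or no precision.

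**What to change.** Make the two sections agree on one covariate list for every Aim 1 and Aim 2 primary model, fixed before outcomes are seen by arm:

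- randomization strata indicators;
- baseline HIV, STI and pregnancy status;
- the baseline value of the outcome analysed, with STI entered only once when it is the outcome.

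Keep QIC for choosing the working correlation structure, and confine QIC-selected covariates to sensitivity analyses. Add two short rules.

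- **Missing baselines.** For example, use the overall mean for a score and a missing category for a status. The rule is needed because when a girl "feels she cannot participate in the biomarker process the interviewer will move on to the next question/part of the interview".
- **Sparse data.** Use one rule, applied blind to arm, that covers both the statuses and rare baseline binary outcomes. For example, omit a factor held by fewer than some stated number of girls in all arms pooled. Word *Selection of Participants* to allow this exception, or the rule would itself break the commitment there.

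Because the Aim 1 analysis targets a marginal effect, report a covariate-standardised marginal odds ratio beside the adjusted one.

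The cost is SAP wording, a few more parameters per model and the standardisation step. No new data are needed: consent to screening and enrollment already covers "having her blood drawn to ascertain HIV, urine testing to determine pregnancy, and high vaginal swab to establish the status on the three STIs", and the baseline assessment is scheduled.

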## Suubi4Her Proposal

Final Version: 7-September-2017

**Study Overview.** The Suubi4Her program will test the effects of a combination asset-based financial inclusion intervention (YDAs) with an evidence-based family strengthening intervention to be delivered via multiple family groups (MFG) to understand the effects and costs associated with a combined intervention versus YDA alone. Specifically, the proposed study addresses three study aims:

**Aim 1.** Examine whether the *Suubi4Her* intervention is effective in protecting adolescent girls against known HIV risk factors (including economically-motivated sex and intimate partner violence).

**Aim 2.** Elucidate the effects of the *Suubi4Her* intervention on behavioral health functioning (i.e., depression, self-efficacy and hopelessness) and examine the effects of these variables as potential mechanisms of change, mediating the relationship between each intervention and HIV risk reduction.

**Aim 3.** Evaluate the cost-effectiveness of each intervention condition.

To address the three aims guiding the proposed study, we will randomize girls (at the school level) to one of three study conditions: 1) YDA condition with a 1:1 saving incentive match rate – for educational purposes and microenterprise development (n=420 participants; n=14 schools); 2) YDA + MFG intervention condition (n=420 participants; n=14 schools); 3) A control condition receiving standard health and sex education provided in schools (n=420 participants; n=14 schools). We detail the three study arms below.

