**Study Population.** A total of 1260 secondary school-going girls (ages 15-17 at enrollment) in their first year of secondary school will be enrolled and followed for the 12 academic terms (through the last year of lower secondary school—Senior 4). To avoid stigma that surrounds being HIV positive in the region, no girl will be excluded by virtue of their HIV status. Rather, girls who test HIV positive during the baseline interviews will be referred for care and support (in the event they are not already in care) to our extensive network of collaborating clinics and NGOs in the study area, depending on the girl's preference. Once a girl has been linked to care, we will follow-up within thirty days to ensure she has been enrolled. We will also verify whether the referred girls are engaged in care during our follow-up interviews. Similarly, girls testing positive for pregnancy will be linked to antenatal care services at an existing health facility of their choice, and will thereafter be followed up by peer mothers for peer support while those testing positive on STIs (Gonorrhea, Trichomonas and Chlamydia) will be linked to STI treatment clinics offering adolescent-friendly services, or to the Rakai Health Sciences Program STD clinic, whichever the participant prefers. Girls will not be excluded for pregnancy status nor STI/STD status.

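### With 14 schools per arm, the uncorrected sandwich standard errors have no small-sample correction or school-based reference distribution; under the usual two-sided Wald z test a nominal .017 comparison runs at about .029

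*Combined protocol and SAP*

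**What the plan says.** The Study Overview states that "we will randomize girls (at the school level) to one of three study conditions" and gives each arm "n=420 participants; n=14 schools". That makes 42 schools, 28 per pairwise contrast, and 420/14 = 30 girls per school on average.

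Under Primary analyses for Specific Aim 1, H1A-H1C are analysed by GEE, using alternating logistic regression (ALR) in SAS PROC GENMOD: "These hypotheses will be tested by three pairwise planned time-averaged comparisons of post-baseline measurements". Each comparison is allotted .05/3 = .017 so that the three together hold .05. On the variance, the section says that robust sandwich "standard errors will be used to obtain correct inferences even if the chosen correlation structure remains slightly misspecified". On the mean model: "Randomization strata indicators will be included as covariates as required by the stratified randomized design to obtain unbiased inferences".

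The Aim 2 paragraph carries the same approach to H2A-H2C and extends the robustness claim to a correlation structure that is "misspecified or if residual distributions are not perfectly normal or homoscedastic".

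Neither paragraph names a test statistic, sidedness, reference distribution, degrees of freedom or small-sample correction. The simulation-based stepdown method is reserved for additional post-hoc comparisons. The case-deletion diagnostics look for influential observations and correct neither the variance nor the reference distribution.

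**The concern.** The stated justification is sound when clusters are many: the sandwich then remains valid although the working correlation is wrong. It says nothing about having few clusters. The independent units here are schools, not the 1260 girls, and at 14 per arm two separate faults arise if the standard error is used in the ordinary Wald way:

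- A normal reference is used where a t with school-based degrees of freedom applies.
- The uncorrected sandwich is biased downward. Without covariates its expectation is 13/14 = .93 of the true variance, and the required stratum indicators increase the bias.

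Both push in the same direction, towards p-values that are too small and intervals that are too narrow. Every confirmatory comparison in Aims 1 and 2 is exposed, and the Bonferroni split would not deliver the family-wise .05 it was chosen for.

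**Working it through.** **Inputs.** Schools per arm m = 14 (Study Overview). Three comparisons at .05/3 (Aim 1 analysis). Two-sided testing and Wald z are assumptions, since the plan states neither. The number of strata, outcome prevalence and intraclass correlation (ICC) are not in the documents and are varied below.

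**The plan's own figure.** .05/3 = .01667, printed as .017. It reproduces. The two-sided normal critical value is 2.394.

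**Closed form: equal schools, no covariates.** The uncorrected sandwich variance of an arm mean is (m - 1)/m times the unbiased between-school variance. The Wald statistic is therefore sqrt(14/13) times a t variable on 2 x 13 = 26 degrees of freedom.

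- Wald z, uncorrected: 2.394 x sqrt(13/14) = 2.307, and P(|t26| > 2.307) = .0293.
- Variance made unbiased, z kept: P(|t26| > 2.394) = .0242.
- Share of the excess due to z instead of t: (.0242 - .0167)/(.0293 - .0167), about 59%. The remainder is variance bias.
- Uncorrected variance with the t26 critical value 2.559: P(|t26| > 2.559 x sqrt(13/14)) = .0206. Neither repair is enough alone.
- At alpha .05: P(|t26| > 1.960 x sqrt(13/14)) = .0701, so a nominal 95% interval covers 93.0%. A nominal 98.3% interval covers 1 - .0293 = 97.1%.

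**Score-type alternative with the same sandwich.** With residuals taken about the pooled mean of 28 schools, S = W²/(1 + W²/28), where W is the uncorrected Wald statistic. S > 2.394² = 5.731 requires W² > 5.731/(1 - 5.731/28) = 7.206, so |t26| > sqrt(7.206 x 13/14) = 2.587. The size is .0156.

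**Strata and family-wise error.** Normal-theory simulation of 42 school means, 200,000 replicates for each assumed number of strata. The corrected columns use the Kauermann-Carroll sandwich with 26 minus the number of stratum indicators as degrees of freedom.

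| Strata (assumed) | Wald z, per test | Wald z, family | Corrected, per test | Corrected, family |
|---|---|---|---|---|
| 1 | .0294 | .075 | .0166 | .044 |
| 2 | .0311 | .079 | .0165 | .044 |
| 3 | .0334 | .085 | .0162 | .043 |
| 4 | .0358 | .090 | .0160 | .042 |
| 5 | .0383 | .096 | .0158 | .042 |

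With 3 to 5 strata the uncorrected sandwich averages .88 to .83 of the true variance, and nominal 95% intervals cover 92.3% to 91.4%. Across 1 to 5 strata the score-type test gives .016 to .022 per test and .041 to .057 family-wise.

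**Binary outcomes.** 10,000 replicates per scenario; 42 schools, 30 girls, 3 waves; prevalence 5% or 20%, ICC .01 or .05, and 1 or 4 strata, all assumed. A logistic GEE with independence working correlation stood in for ALR. Wald z ran at .030 to .044 per test. The corrected test ran at .016 to .022, family-wise .043 to .056, with the highest values at 5% prevalence and ICC .05.

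**The case against.** The strongest reply is that the plan never says Wald z. It names a standard error and leaves the test open. On a score-type reading the p-values are close to nominal, so the documents establish an unspecified test, not an inflated one. That stands as a limit: the inflation is conditional. It does not remove the point, because a standard error is ordinarily turned into a Wald test and interval, and Wald intervals undercover whichever test supplies the p-value. Two analysts following the same text could test at about .016 or at .03 to .038.

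Next, .029 is the no-covariate case, while the plan requires stratum indicators and their number is unknown. That is fair, but in every setting tried the indicators raised the error, so .029 is near the low end.

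Third, the remedy was checked on an independence GEE and not on ALR with a structure chosen by QIC. ALR's mean model is itself a GEE, so the correction applies, but its availability in the named procedure needs confirming.

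Fourth, the remedy is not exact. Besides the .022 seen with a rare outcome, unequal school sizes matter. With assumed coefficients of variation of .4 and .7, the corrected test ran at about .018 to .019 and .022, against .033 and .040 for Wald z. It remains clearly better.

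Finally, other corrections would serve. That is true: the necessary step is to fix the statistic, sidedness, correction and degrees of freedom in advance.

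**Conclusion.** The concern holds and should be fixed. The plan rests its inference on an uncorrected sandwich with 14 schools per arm and supplies nothing to handle the small number of clusters. Under a two-sided Wald z test, with equal school sizes, equal between-school variance and no covariates, each comparison runs at .0293 instead of .0167, and the family of three at about .075 instead of .05. With 3 to 5 assumed strata the figures are .033 to .038 and .085 to .096. The closed-form .0293 does not depend on any assumed prevalence or ICC. The consequence is moderate and conditional on a test the plan leaves open, but it reaches all of H1A-H1C and H2A-H2C and could decide a borderline result.

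**What to change.** In both the Aim 1 and Aim 2 paragraphs, replace the sandwich sentence with wording such as:

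> Standard errors will be the Kauermann-Carroll bias-corrected sandwich with school as the cluster. Each pairwise contrast will be tested two-sided by a Wald statistic, and its confidence interval formed, using a t distribution with 28 - 2 - (number of stratum indicators) degrees of freedom.

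State the number of strata, and confirm that the correction can be computed for the ALR fit before outcome comparisons are seen. Degrees of freedom of 42 minus the number of school-level parameters are less cautious: about .019 per test and .05 family-wise in normal theory, but up to .025 per test in the binary check. A permutation test of school allocation within strata is a useful optional sensitivity analysis.

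The cost is a sentence in each paragraph plus programming. Intervals at the .017 level widen by (2.559/2.394) x sqrt(14/13) = 1.109, about 11%, with no strata, and by about 15% to 19% with 3 to 5. At an effect that would have 80% power with known variance, power is about 74% to 75%, against about 82% to 85% for the oversized Wald test. Part of that difference is the price of valid size. Estimates, design and sample size do not change.
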